7.2.2. EORTC QLQ-OV28

Effective with Amendment 2, EORTC QLQ-OV28 will no longer be performed/collected.

The EORTC QLQ-OV-28 is the ovarian cancer-specific module of the EORTC quality of life questionnaire.^{35,36} The EORTC QLQ-OV-28 is a 28 item instrument with seven (7) functional domain subscales. The 7 subscales include: (i) an abdominal/gastrointestinal symptom subscale (7 items); (ii) a peripheral neuropathy subscale (3 items); (iii) an other chemotherapy side effects subscale (7 items); (iv) a hormonal/menopausal symptoms subscale (2 items); (v) a body image subscale (2 items); (vi) an attitude to disease and treatment subscale (3 items) and (vii) a sexual function subscale (4 items). Similar to the EORTC QLQ-C30 higher scores are reflective of a greater presence of symptoms.

7.2.3. EQ-5D-5L

Effective with Amendment 2, EQ-5D-5L will no longer be performed/collected.

The EQ-5D-5L is a patient-completed questionnaire designed to assess health status in terms of a single index value or utility score.^{37,38,39} There are 2 components to the EQ-5D-5L: a Health State Profile which has individuals rate their level of problems (none, slight,

moderate, severe, extreme/unable) in 5 areas (mobility, self-care, usual activities, pain/discomfort, and anxiety/depression) and a Visual Analogue Scale (VAS) in which patients rate their overall health status from 0 (worst imaginable) to 100 (best imaginable). Published weights are available that allow for the creation of a single summary score.³⁹

7.3. Pharmacokinetic Assessments

Effective with Amendment 2, pharmacokinetic assessments will no longer be performed/collected.

7.3.1. Blood Sample Collection for Pharmacokinetic Analysis

Effective with Amendment 2, blood sample collection for pharmacokinetic analysis will no longer be performed/collected.

7.3.2. Immunogenicity Assessment

Effective with Amendment 2, immunogenicity assessments will no longer be performed/collected.

7.4. Translational and Pharmacodynamic Assessments

Effective with Amendment 2, translational and pharmacodynamic assessments will no longer be performed/collected.

7.4.1. Archived Tumor Biospecimens and De Novo Tumor Biopsies

Effective with Amendment 2, tumor samples will no longer be collected.

Archived tumor tissue samples and *de novo* biopsies of primary and/or metastatic lesions (see [Section 6.1.1](#)) will be used to analyze candidate DNA, RNA, or protein markers, or relevant signature of markers for their ability to identify those patients who are most likely to benefit from treatment with the study drugs.

Markers that may be analyzed include, but may not necessarily be limited to, the presence/absence of tumor-infiltrating CD8⁺ T lymphocytes and/or expression of PD-L1, FoxP3, PD-1, PD-L2 within the tumor microenvironment by immunohistochemistry.

Optional tumor biopsies obtained upon disease progression may be assessed relative to the mandatory pre-treatment biospecimens to examine tumoral and immunological changes which may occur over the course of therapy, including acquired mechanisms of resistance.

7.4.2. BRCA 1/2 Mutation Status

Effective with Amendment 2, BRCA 1/2 mutation status assessment is no longer required per protocol but may be performed as clinically necessary and need not be recorded in OC-RDC.

Please refer to the new SOA in [Appendix 7](#).

7.5. Banked Biospecimens

7.5.1. Markers of Drug Response

Effective with Amendment 2, additional collection of banked biospecimens are no longer necessary. Please refer to the new SOA in [Appendix 7](#).

Studying the variation in genetic markers and other biomarkers may help to explain some of the variability in response seen with some drugs among different individuals. This is referred to as pharmacogenomic/biomarker research. Comparing the DNA, RNA, protein, and metabolite variation patterns of patients who respond well and those who respond poorly to treatment may help to better define the most appropriate group of patients in which to target a given treatment. Collecting biospecimens for exploratory pharmacogenomic/biomarker analyses and retaining them in the Pfizer BioBank makes it possible to better understand the drug's mechanism of action and to seek explanations for differences in, for example, exposure, efficacy, tolerability, or safety not anticipated prior to the beginning of the study. Providing these biospecimens is a required study activity for study sites and patients, unless prohibited as such by local regulations or ethics committee decision.

To protect patients' confidentiality, the banked biospecimens and data generated from them will be coded with the patient's study identification (ID) number. Samples will be kept in a facility accessible only by badge-swipe. Data will be stored on password-protected computer systems. The key between the code and the patient's personal identifiers will be held at the study site; the researchers using the biospecimens and data generated from them will not have access to the key nor any personally identifying information. Biospecimens will only be used for the purposes described here and in the informed consent document/patient information sheet; any other uses require additional ethical approval. Unless a time limitation is required by local regulations or ethical requirements, biospecimens will be stored indefinitely to allow for future research on the topics described here, including research conducted during the lengthy drug development process and also post-marketing research. Patients can withdraw their consent for the use of their biospecimens at any time by making a request to the Investigator, in which event any remaining biospecimen will be destroyed; data already generated from the biospecimens will continue to be stored to protect the integrity of existing analyses. It is very unlikely that results generated from the biospecimens will have any clinical, diagnostic, or therapeutic implications for the individual study participants. Patients are notified in the informed consent document/patient information sheet that their results will not be given to them, unless required by local laws or regulations, in which case results will be returned via the Investigator. Results will not be provided to family members or other physicians; nor will they be recorded in the patient's medical record. There is no intention to contact patients after completion of the clinical trial.

It is possible that the use of these biospecimens may result in commercially viable products. Patients will be advised in the informed consent document/patient information sheet that they will not be compensated in this event.

7.5.2. Additional Research

Unless prohibited by local regulations or ethics committee decision, patients will be asked to indicate on the consent form whether they will allow the banked biospecimens to also be used for the following research:

- Investigations of the disease under study in the clinical trial, and related conditions.
- Biospecimens may be used as controls. This includes use in case-control studies of diseases for which Pfizer is researching drug therapies; use in characterizing the natural variation amongst people in genes, RNA, proteins, and metabolites; and use in developing new technologies related to Pharmacogenomics/biomarkers.

Patients need not provide additional biospecimens for the uses described in this section; the biospecimens specified in [Section 7.5.1](#) will be used. Patients may still participate in the clinical trial if they elect not to allow their banked biospecimens to be used for the additional purposes described in this section.

7.6. Tumor Response Assessments

Please refer to the new SOA in [Appendix 7](#).

Tumor assessments will include all known or suspected disease sites. Imaging will be conducted per the local site's standard of care and need not be recorded in OC-RDC, unless the findings support an AE.

Brain CT or MRI scan at baseline is only required when there are suspected brain metastases or new lesion during the study.

Bone scan (bone scintigraphy) or ¹⁸F-FDG-PET/CT are only required at baseline if bone metastases are suspected. Otherwise, bone imaging is required only if new bone metastases are suspected.

The same imaging technique used to characterize each identified and reported lesion at baseline should be employed in the following tumor assessments.

In addition, radiological tumor assessments will also be conducted whenever disease progression is suspected (eg, symptomatic deterioration). Assessment of response will be made using RECIST version 1.1 ([Appendix 3](#)). All patients' files and radiologic images will be collected by Parexel.

7.7. Expedited Blinded Independent Central Review for Disease Progression

Effective with Amendment 2, BICR will no longer be utilized, however all scans will continue to be sent to Parexel for storage.

8. ADVERSE EVENT REPORTING

8.1. Adverse Events

All observed or volunteered AEs regardless of study treatment or suspected causal relationship to the study treatment(s) will be reported as described in the following sections.

For all AEs, the Investigator must pursue and obtain information adequate both to determine the outcome of the AE and to assess whether it meets the criteria for classification as an SAE requiring immediate notification to Pfizer or its designated representative. For all AEs, sufficient information should be obtained by the Investigator to determine the causality of the AE. The Investigator is required to assess causality. Follow-up by the Investigator may be required until the event or its sequelae resolve or stabilize at a level acceptable to the Investigator, and Pfizer concurs with that assessment.

As part of ongoing safety reviews conducted by the Sponsor, any non-serious adverse event that is determined by the Sponsor to be serious will be reported by the Sponsor as an SAE. To assist in the determination of case seriousness further information may be requested from the Investigator to provide clarity and understanding of the event in the context of the clinical trial.

8.2. Reporting Period

For SAEs, the active reporting period to Pfizer or its designated representative begins from the time that the subject provides informed consent, which is obtained prior to the subject's participation in the study, ie, prior to undergoing any study-related procedure and/or receiving investigational product, through and including 90 calendar days after the last administration of the study treatment.

SAEs occurring to a subject after the active reporting period has ended should be reported to the sponsor if the investigator becomes aware of them; at a minimum, all SAEs that the investigator believes have at least a reasonable possibility of being related to study treatment are to be reported to the sponsor.

AEs (serious and non-serious) should be recorded on the case report form (CRF) from the time the subject has taken at least 1 dose of study treatment through 90 calendar days after the last administration of the study treatment.

If a patient begins a new anticancer therapy, the AE reporting period for nonserious AEs ends at the time the new treatment is started. Death must be reported if it occurs during the SAE reporting period after the last dose of study treatment, irrespective of any intervening treatment.

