7.1.2. Adverse Events

7.1.2.1. Adverse Events of Special Interest for Avelumab

- Any AE that is suspected to be a potential irAE is considered an AE of special interest (AESI). Specific guidance for the management of immune-related AEs is provided in [Section 5.2.7.2.3](#), [Appendix 9](#) Avelumab Management of Immune-related Adverse Events. AESIs are reported according to the general AE reporting rules specified in [Section 8.2](#).

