5.2.7. Definition of on-treatment period

Safety endpoints will be summarized based on the on-treatment period unless otherwise specified.

On-treatment period is defined as the time from the first dose of study treatment through minimum (30 days + last dose of study treatment, start day of new anti-cancer drug therapy – 1 day).

Safety data collected outside the on-treatment period as described above will be listed and flagged in listings but will not be summarized.

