6.6.1. Adverse events

Treatment-emergent adverse events (TEAEs) are those events with onset dates occurring during the on-treatment period for the first time, or if the worsening of an event is during the on-treatment period as defined in Section 3.5.1.

All analyses described will be based on TEAEs (started during the on-treatment period) if not otherwise specified. The AE listings will include all AEs (whether treatment-emergent or not). AEs outside the on-treatment period will be flagged in the listings.

- **Related Adverse Events:** adverse events with relationship to study treatment (as recorded on the AE eCRF page, Relationship with study treatment = Related) reported by the investigator and those of unknown relationship (ie, no answer to the question ‘Relationship with study treatment’). Related AEs are those related to any study drug (ie, at least one of the study drugs).
- **Serious Adverse Events (SAE):** serious adverse events (as recorded on the AE eCRF page, Serious Adverse Event = Yes).
- **Adverse Events Leading to Dose Reduction:** adverse events leading to dose reduction of study treatment (as recorded on the AE eCRF page, Action taken with study treatment = Dose reduced).
- **Adverse Events Leading to Interruption of Study Treatment:** adverse events leading to interruption of study treatment (as recorded on the AE eCRF page, Action taken with study treatment = Drug interrupted). The eCRF does not allow for a clear separation between interruption of an infusion and delays of administration for a parenteral drug as both are recorded using the same term on the eCRF (“Drug interrupted”). IRRs will be excluded in the analysis of AEs leading to Drug Interruption in case they only led to an interruption of the infusion.
- **Adverse Events Leading to Permanent Treatment Discontinuation:** adverse events leading to permanent discontinuation of study treatment (as recorded on the AE eCRF page, Action taken with study treatment = Drug withdrawn).
- **Adverse Events Leading to Death:** adverse event leading to death (as recorded on the AE eCRF page, Outcome = Fatal, as well as AEs of Grade 5).
- **Immune-related Adverse Events (irAE):** irAEs (as identified according to the methodology outlined in Appendix 1 for a pre-specified search list of MedDRA PTs, documented in the Safety Review Plan and finalized for analysis of the current studies data prior to DB lock)

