9. APPENDICES

Appendix 1. Immune-Related Adverse Events

The MedDRA PTs and clusters for irAEs are defined in the Safety Review Plan (SRP) for avelumab.

Immune-related AEs (irAEs) will be programmatically identified as outlined in Table 16. This case definition is hierarchical, ie, each step is only checked for patients and events that have already met the prior step.

Table 16. Case Definition for irAEs

Step	Selection Criteria	Additional Notes
1	Event selected based on a list of pre-specified MedDRA PTs within clusters. These are included in the SRP as Tier1 events (Immune-mediated xxxx). If AE matches the list then it is in for the next step	
2	AE onset during 1 st study drug administration or anytime thereafter through 90 days after last dose of study treatment.	This is regardless of start of new anti-cancer drug therapy and regardless of TEAE classifications
3	Answer in the AE eCRF page to ‘Was another treatment given because of the occurrence of the event’ is ‘YES’	
4	AE treated with corticosteroids or other immunosuppressant therapy. For endocrinopathies only: AE required hormone replacement	Look in the conmed pages for AE identifiers that match the AEs from Step 3. For each of such AEs if A) OR B) below are met then the AE is in for the next step A) conmed ATC code is in (H02A, H02B, H02C, D07, A01AC, S01BA, S01BB, L04AA, L04AB, L04AC, L04AD, L04AX) and AE PT is in any of the irAE clusters. B) conmed ATC code is in (H03A, H03B) and AE PT is in one of the irAE clusters associated with “Immune-mediated endocrinopathies”

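### The SAP counts immune-related AEs to day 90 regardless of new anti-cancer drug therapy, but the protocol stops collecting non-serious ones when new therapy starts

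*Protocol*

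**What the plan says.** Protocol 8.2 has SAEs actively reported from consent "through and including 90 calendar days after the last administration of the study treatment". All AEs go on the CRF from first dose to the same day-90 limit, with one exception: "If a patient begins a new anticancer therapy, the AE reporting period for nonserious AEs ends at the time the new treatment is started". No such cut-off is stated for SAEs.

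Protocol 7.1.2.1 makes every suspected irAE an AE of special interest and says "AESIs are reported according to the general AE reporting rules specified in" Section 8.2. It makes no exception for them.

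SAP Appendix 1, Table 16, Step 2 accepts an irAE with onset at first study drug administration or "anytime thereafter through 90 days after last dose of study treatment". The note beside it adds: "This is regardless of start of new anti-cancer drug therapy and regardless of TEAE classifications". Steps 3 to 5 then require that the event was treated (corticosteroids, other immunosuppressants or, for endocrinopathies, hormone therapy) and that it passes a check for another cause.

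SAP 6.6.4 reports irAEs, Grade 3 or higher irAEs and serious irAEs by arm. For the first two it adds risk differences, 95% CIs and p-values against the comparator arm.

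**The concern.** The SAP deliberately chose a window for irAEs that new drug therapy does not close. The protocol's collection rule cannot fill that window for non-serious events. After a switch, a count of zero non-serious irAEs means that the protocol did not ask for them, not that none occurred. The tables would place serious and non-serious irAEs side by side as if both had been observed for the same time.

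At stake is the completeness of the between-arm irAE comparison. How long non-serious irAEs are recorded after last dose depends on when the patient starts the next therapy. That is a post-randomization event and may differ between arms.

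**Working it through.** The plan states no figure on this point, so the check is mainly a comparison of texts.

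**1. Collection against counting, for an event with onset within 90 days of last dose**

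| Onset | Serious irAE | Non-serious irAE |
|---|---|---|
| Before new therapy | collected (8.2); counted (Table 16) | collected; counted |
| After new therapy | collected; counted | **not collected**; would be counted |

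Only the bottom right cell is in conflict.

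**2. Do other SAP rules remove the conflict?** SAP 6.6.1 says "All analyses described will be based on TEAEs (started during the on-treatment period) if not otherwise specified", and SAP 5.2.7 ends the on-treatment period at the earlier of 30 days after last dose and the day before new anti-cancer drug therapy. Both are defaults that allow exceptions, and Table 16 is an explicit exception. The medical review at the end of Appendix 1 can add cases that the algorithm missed, but not events that were never recorded.

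**3. Are such events to be expected?** The background data suggest so:
- Protocol 1.2.2.4: 8 of 75 patients in the ovarian cohort had immune-related TEAEs (hypothyroidism 5, arthritis 2, myositis 1). None of these terms is among the related serious TEAEs listed there, while arthritis and myositis are among the Grade 3 related events.
- Protocol 1.2.2.2: of 69 potential irAEs in the Phase 1 study, 26 were Grade 1 and 29 Grade 2; (26 + 29)/69 = 80%.
- Both versions of the Schedule of Activities test ACTH, free T4 and TSH at the Day 30, 60 and 90 visits. The plan therefore looks for endocrine irAEs to day 90 in patients for whom 8.2 may no longer call for a resulting non-serious AE to be recorded.

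**4. Illustration of size (assumed inputs).** Suppose that time from last dose to next therapy is exponential with median m days, ignoring deaths. With λ = ln 2/m:
- proportion switching within 90 days = 1 − exp(−90λ)
- mean share of the 90 post-dose days still open to non-serious collection = [1 − exp(−90λ)]/(90λ)

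| m (days) | 90λ | switch by day 90 | share open |
|---|---|---|---|
| 30 | 2.079 | 87.5% | 42% |
| 60 | 1.040 | 65% | 62% |
| 90 | 0.693 | 50% | 72% |
| 120 | 0.520 | 40% | 78% |
| 180 | 0.347 | 29% | 85% |

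This covers the post-dose part only, and the Table 16 window starts at first dose. For one patient treated for T days who switches s days after last dose, the recorded share of the whole window is (T + s)/(T + 90). Take T as the planning median PFS (3.5 months ≈ 107 days, 5.8 months ≈ 177 days) and assume s = 21 to 60:
- lowest: (107 + 21)/(107 + 90) = 128/197 = 65%
- highest: (177 + 60)/(177 + 90) = 237/267 = 89%

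It is 100% for a patient who does not switch within 90 days. These are shares of time, not of events.

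**The case against.** The strongest reply is that the two rules can coexist: the SAP counts whatever was collected, and stopping non-serious collection at the next therapy is a reasonable way to avoid events confounded by another drug. The affected class is also narrow. Table 16 never counts untreated events, important medical events are reported as serious under Protocol 8.6, and the sponsor may upgrade events under 8.1. SAP 6.6.4 calls its p-values unadjusted and for screening only, and SAP 3.5.1 treats safety analyses as generally exploratory. The irAE listing already flags onset outside the on-treatment period.

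Most of this stands as a limit on importance. It does not close the gap. The attribution argument supports the protocol's rule, but the SAP set that rule aside for irAEs, so the documents make opposite choices. A listing flag marks only events that exist in the database.

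A reader might also infer that the arm with faster progression will look safer. The documents do not support that. Faster progression shortens time on treatment, which affects any crude incidence table with or without this clause; the clause acts only on the interval from last dose to next therapy, which is not given by arm or tied to PFS. Nor do they support a claim that the serious share of irAEs is inflated in a planned result, since the SAP specifies no serious-to-total ratio.

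**Conclusion.** The inconsistency is confirmed on the text. Treated, non-serious irAEs with onset after new anticancer therapy and within 90 days of last dose are in the SAP's window but not in the protocol's collection, while serious ones are in both. The irAE and Grade 3 or higher irAE counts and risk differences are therefore incomplete for patients who switch within 90 days. Patients who do not switch in that time, and serious irAEs, are unaffected.

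The size depends on time to next therapy. Under the assumptions above, 65% to 89% of the whole window is recorded in a patient who switches. A figure such as 30/90 = 33% would describe only the post-dose part, for an assumed switch at day 30, and should not be read as the share of all irAE follow-up. The direction of any between-arm effect is unknown. This should be corrected or disclosed, but no confirmatory conclusion rests on it.

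**What to change.** **Collection.** In Protocol 8.2, exempt suspected irAEs (AESIs) from the new-therapy cut-off, so that serious and non-serious ones are both recorded through day 90, with a flag for onset after new therapy. The Day 30, 60 and 90 visits and endocrine tests already exist, so the added burden is small, though it needs a protocol amendment. The drawback is that some late events will be confounded by the next drug; the flag lets the analyst separate them. Because the final analysis is complete, this helps only patients still on treatment in Arms A and B and cannot repair the comparison with Arm C.

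**Data already collected.** Keep the Table 16 analysis. State in the irAE tables that non-serious events after new anticancer therapy were not collected. Add a sensitivity table of all irAEs with onset before the earlier of day 90 and new anticancer therapy, and show later serious irAEs separately. Use the trigger in 8.2, which is any new anticancer therapy; the broader definition in SAP 5.2.6 is closer to it than the drug-only one in 5.2.5. The cost is one footnote and one extra table.

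The truncated table should not replace the main analysis. Recording time would still depend on time to switch, now for serious irAEs too, and fully collected serious events would leave the comparison.
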